The overall study period will be between 2010 and 2020. Different study period starts will be applied depending on which two drugs are being compared. For the comparison between rhFSH-alfa reference product and HP-hMG, the study period will start 1 January 2010 for both countries. This date is selected to ensure the study is sufficiently powered while also reducing heterogeneity in patient management over time. Changes that have occurred over time include moving towards vitrification rather than slow freezing for embryo cryopreservation and hence also moving from cleavage stage to blastocyst embryo transfers, elective single embryo transfers rather than double embryo transfers, and antagonist protocols rather than agonist protocols. For the comparison between rhFSH-alfa reference product and rhFSH-alfa biosimilar products, the study period will start 26 March 2014 for Denmark and 20 June 2014 for Sweden. These are the earliest dates when a rhFSH-alfa biosimilar product (Bemfola) received reimbursement status in each country. For

Sweden, where the IVF register is updated annually and has a lag time of approximately two years (see Section 9.4.2), inclusion of women undergoing IVF/ICSI treatment may end on 31 December 2019, depending on data availability at the time of data extraction. No such general restriction will be applied for Denmark, as the IVF register is updated monthly. In terms of follow-up of IVF/ICSI treatment and pregnancy outcomes, the study will end on 31 December 2020 (or last available date) for each country. Specifically, for the main analyses of the primary objective (LBR, CLBR and MC-CLBR) and secondary objective 4 (TTLB), a minimum follow-up period of 1 year has been chosen to allow sufficient time to achieve (at least) one live birth and a reasonable number of complete cycles for reliable estimates of live birth rates. Hence, the corresponding analyses are restricted to cycles initiated on or before 31 December 2019 (Sets 1 and 5 in Table 5). The minimum follow-up period will be extended to 2 years in a sensitivity analysis to explore the potential effect this has on the estimated MC-CLBR and TTLB (see sensitivity analysis 3 in Table 8).

To reduce possible bias linked to confounding by baseline characteristics, inverse probability of treatment weighting (IPTW), based on propensity scores (PS) (22), will be used to balance the distribution of potential confounders across the study cohorts.

Figure 1. Study design

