9.3.2 Other Variables (Covariates)

In addition to the outcome and exposure variables outlined in Section 9.1.2 and Section 9.3.1, the covariates of interest in this study are listed below and classified according to their intended use in the analysis (Table 1).

The variables are generally described as measured in relation to each IVF/ICSI stimulation cycle; however, variables used to derive the outcome variables may also apply to any linked FET cycles, depending on the outcome under study. Variables indicated as being candidates for regression modeling are determined after the decision on which gonadotropin to use for COS has been made. These variables will therefore not be included in the PS but may instead be added as independent covariates in the IPTW-weighted regression model (see Section 9.7.3.1 for further details).

For variables identified in the registers by ATC, ICD-10 and/or procedure codes, these operational definitions are provided in Appendix 3 (Section 14.3.3).

Table 1. List of covariates and their use in the study

Variable	Measurement scale	Baseline characteristic	Candidate variable for PS	Candidate variable for additional adjustment
Demographic characteristics				
Age at stimulation cycle index date	Continuous	X	X	
IVF/ICSI treatment characteristics				
Treatment type (ICSI, IVF, ICSI + IVF; FET)	Categorical	X	X	
Type of clinic (private, public)	Categorical	X	X	
Calendar year of stimulation cycle	Continuous	X		
GnRH protocol (agonist, antagonist)	Categorical	X	X	
Cycle cancellation (timing within cycle)	Categorical	N/A (used to derive outcome variable)		
Date of cycle cancellation	Continuous	N/A (used to derive outcome variable)		
Type of drug for ovulation triggering	Categorical	X		X

Variable	Measurement scale	Baseline characteristic	Candidate variable for PS	Candidate variable for additional adjustment
Type of drug for luteal phase support	Categorical	X		X
Date of follicular aspiration	Continuous	N/A (used to derive outcome variable)		
Date of embryo transfer	Continuous	N/A (used to derive outcome variable)		
Number of days of embryo cultivation ⁺	Numerical	X		X
Date of embryo cryopreservation	Continuous	N/A (used to derive outcome variable)		
Embryo cryopreservation method (slow freezing, vitrification)	Categorical	X		X
Date of embryo thawing	Continuous	N/A (used to derive outcome variable)		
Number of embryos thawed	Continuous	N/A (used to derive outcome variable)		

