9.7.3.1 Propensity Score Methodology

PS-based methods are frequently used in non-interventional studies to control for confounding when estimating treatment effects (38). In this study, the PS weighting will be implemented using IPTW approach.

PS, typically obtained using logistic regression models, are covariate summary scores that indicate the individual probability of having a treatment initiated with the study drug against the comparator drug, given the observed baseline characteristics. In PS weighting with IPTWs, each subject is weighted by the inverse probability of receiving the treatment they have actually received, *i.e.*, $1/PS$ in the study drug cohort and $1/(1-PS)$ in the comparator drug cohort (22). In other words, the PS weighting with IPTW creates a pseudo-population of study drug cohort and the comparator drug cohort that are weighted samples of the original study cohorts but have the same covariate distribution as the overall original study cohorts (22). Thus, using the IPTW-weighted study cohorts will remove confounding from all covariates included in the PS model, and give the estimate for the treatment effect in the overall population (22).

For this study, the IPTW approach will be based on pairwise PS estimation for i) rhFSH-alfa reference product cohort and HP-hMG cohort, and ii) rhFSH-alfa reference product cohort and rhFSH-alfa biosimilars cohort. The PS will be estimated for the stimulation cycle initiation with the study drug (rhFSH-alfa reference product) against the comparator drug (HP-hMG or rhFSH-alfa biosimilar product) by using logistic regression, including covariates as indicated in Table 1 (Section 9.3.2). Based on the estimated pairwise PS, i) IPTW-weighted rhFSH-alfa reference product cohort and IPTW-weighted HP-hMG cohort, as well as ii) IPTW-weighted rhFSH-alfa reference product cohort and IPTW-weighted rhFSH-alfa biosimilars cohort will be created.

Diagnostic measures will be used for assessing the success of the PS model to account for confounding. In addition, the distribution of IPTWs will be checked and in case very large weights are observed, the stabilized, trimmed and truncated weights will be considered to avoid increasing the variability of the treatment effect estimates due to very large weights (38).

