9.7.3.4 Adjusted Odds Ratios

For the comparison of the study cohorts, the ORs (with 95% CI), adjusted for confounding factors, will be estimated by taking into account the IPTWs and using statistical modelling, such as regression analysis or general estimating equations. To estimate the adjusted ORs, the statistical model will be weighted with IPTWs and will include as covariates any variables that were used in the PS but are still unbalanced between the study cohorts after weighting. Statistical models may also be used to additionally adjust the ORs for any other potential covariates that are assessed after the initiation of the IVF/ICSI stimulation cycle and hypothesized to be associated with the given study outcomes (see Table 1 in Section 9.3.2).

For the statistical models, the following study outcomes will be considered as binary outcomes analyzed per fresh embryo transfer: live birth (*i.e.*, a primary objective outcome), clinical pregnancy and ongoing pregnancy (*i.e.*, a subset of secondary objective 1 outcomes). For the statistical models, the following study outcomes will be considered as binary outcomes analyzed per woman: MC-CLBR (*i.e.*, a primary objective outcome) will be analyzed as a binary outcome per woman in statistical models.

For the statistical models, the following study outcomes will be considered as binary outcomes analyzed per clinical pregnancies following fresh or frozen embryo transfer: pregnancy loss (secondary objective 5) and multiple pregnancy (secondary objective 6). Cycle cancellation (secondary objective 7) and OHSS occurrence (secondary objective 8) will be analyzed as binary outcomes per initiated stimulation cycle. Implantation (secondary objective 3) will be analyzed as an ordinal categorical outcome per fresh or frozen embryo transfer.

For the statistical models, the following study outcomes are considered as counts analyzed per initiated stimulation cycle: cumulative live birth (*i.e.*, a primary objective outcome), cumulative clinical pregnancy and cumulative ongoing clinical pregnancy (*i.e.*, a subset of secondary objective 1 outcomes). Also the following study outcomes are considered as counts in statistical models and

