the Danish National Board of Health suspected that were to some degree an under ascertainment of the true number of treatments initiated due to incomplete capture, noting that the use of electronic capture in future updates would improve quality (55,56). However, as only electronic reports are included during the period under study (2010-2020), previously identified limitations related to underreporting would not be an issue in this study. All treatment cycles and measurements on pregnancies from private and public IVF clinics are required to be reported, and the DIVF during the study period is based on electronic capture and complete and validated data (52). Similar to the Q-IVF, the DIVF has been used extensively in research (27,40,54,57,58).

As in any study assessing cumulative live birth rates of IVF treatment, uncertainty remains around end outcomes in those who discontinued treatment, had they continued. This uncertainty will be addressed by the estimation of conservative estimates and, in a sensitivity analysis, optimal estimates for the primary objective MC-CLBR outcome, based on different assumptions of live birth rates in women who discontinued treatment (see Analysis 2 in Table 8). Similarly, the impact on the conservative and optimal MC-CLBR estimates of extending the minimum follow-up to 2 years will also be explored (see Analysis 3 in Table 8).

Further, prescribing patterns of the study drugs are likely to vary to some extent across the study period. If one drug was favored over the other in the early part of the study period, the probability of observing all live births in up to five stimulation cycles using that drug would be higher than for the other one (due to availability of data with longer follow-up). Based on the feasibility assessment of the use of the study drugs in Denmark and Sweden, it is known that the use of rhFSH-alfa biosimilar products has increased gradually, with a relatively larger proportion observed during the latter part of the study period, compared with rhFSH-alfa reference product (37). Hence, it cannot be ruled out that this may lead to a downward bias for the cumulative live birth rate outcomes following COS with rhFSH-alfa biosimilar products.

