Prior to October 2016, induced abortions were not recorded in the SNPR, meaning ascertainment of this component of pregnancy loss will rely solely on the Q-IVF prior to this date. Furthermore, abortion statistics based on anonymized data show that ~70% of all induced abortions between 2018 and the second quarter of 2020 were medical abortions completed at home (59). This suggests the data on induced abortions captured in the SNPR in 2016-2020 is likely incomplete.

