9.9.5 Study Size and Time Trends

The study size depends on the inclusion period and the incidence of fertility treatments in both countries of study. Differences in standard of care, treatment patterns and success rates are expected to some extent over time. Legal regulations on eligibility for IVF treatment (e.g., donor gametes, lesbian couples, single women) and rules for storage of frozen oocytes and embryos have also changed during the study period. However, with an overall study period spanning 11 years from 2010-2020, any changes in standard of care are expected to have limited impact on the consistency of results across the study period.

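### Calendar year enters neither the propensity score nor the outcome models, so the reference versus biosimilar comparison is open to time trends the protocol itself describes

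*Protocol*

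**What the plan says.** Protocol 9.3.2, Table 1, has separate columns for baseline characteristics, PS candidates and candidates for additional adjustment. The row "Calendar year of stimulation cycle" is marked in the first column only. The neighbouring rows for type of clinic and GnRH protocol are also marked for the PS.

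Section 9.7.3.1 estimates each pairwise PS from the covariates indicated in Table 1. Section 9.7.3.4 says the weighted outcome model "will include as covariates any variables that were used in the PS but are still unbalanced between the study cohorts after weighting". It also allows optional adjustment for Table 1 covariates assessed after the cycle has started. The Cox model in 9.7.3.5 follows the same rule, and 9.7.3.6 stratifies by age and GnRH protocol only.

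On time trends:
- 9.9.2 says "prescribing patterns of the study drugs are likely to vary to some extent across the study period" and, for biosimilars, "use of rhFSH-alfa biosimilar products has increased gradually, with a relatively larger proportion observed during the latter part of the study period".
- 9.1.1 says "Changes that have occurred over time include moving towards vitrification rather than slow freezing for embryo cryopreservation", and also names blastocyst transfer, elective single embryo transfer and antagonist protocols.
- 9.9.5 expects success rates to differ to some extent over time, but concludes that "any changes in standard of care are expected to have limited impact on the consistency of results across the study period".

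**The concern.** A variable that precedes treatment and is related to both drug choice and outcome belongs in the PS. By the protocol's own account, calendar year is such a variable for the biosimilar comparison. The reason 9.3.2 gives for keeping some variables out of the PS is that they are determined after the gonadotropin is chosen. That does not apply to calendar year, and no other reason is given.

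The weighted cohorts could then balance on every PS covariate and still set earlier reference cycles against later biosimilar cycles. Because year is not a PS variable, residual imbalance in it would not trigger adjustment either. Any drift in live birth would be read as a drug effect.

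There is a second route for cumulative outcomes. Follow-up ends on a fixed date, the CLBR set counts only linked frozen transfer cycles started by 31 December 2019 (9.7.1, Set 2), and the main MC-CLBR analysis treats women who do not return as having no live birth (9.7.3.3). Later cycles have less time to accrue births. Section 9.9.2 concedes a possible downward bias for biosimilars on this account.

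**Working it through.** **1. The plan's own yardstick (9.5).** Inputs: 75% of the anticipated women, comparator MC-CLBR 50%, and the criterion that the lower 95% limit of the odds ratio exceeds 1. The smallest such difference solves ln(OR) = 1.96 × √(1/(n₁p₁q₁) + 1/(n₂p₂q₂)).
- Denmark, biosimilars: 0.75 × 14,000 = 10,500 and 0.75 × 3,000 = 2,250 women give 2.28 points.
- Sweden, biosimilars: 0.75 × 11,000 = 8,250 and 0.75 × 10,000 = 7,500 women give 1.57 points.

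Rounded up to the Table 3 grid, these are the stated 2.5 and 2.0 points. They serve here only as a scale for bias.

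**2. Length of the biosimilar window (9.2.3, 9.7.1).** From the start date to 31 December 2019, L = 5.77 years in Denmark (from 26 March 2014) and 5.53 years in Sweden (from 20 June 2014).

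**3. Gap in mean cycle date.** Assumption: biosimilar use rises linearly from zero, so its mean date is 2L/3.
- If reference use is flat (mean L/2), the gap is L/6: Denmark 5.77/6 = 0.96 years, Sweden 5.53/6 = 0.92 years.
- If biosimilars displace only the reference product and the two together stay constant, the gap is (L/6)(1 + B/R), where B and R are the Table 2 cycle totals. Denmark: 0.96 × (1 + 5,000/31,000) = 1.12 years. Sweden: 0.92 × (1 + 18,000/22,000) = 1.68 years.

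The Swedish upper value is a ceiling. It needs a reference share starting at 40,000/65,000 = 62% of cycles in 2014, whereas Table 2 and 9.5 imply (42,000 − 22,000)/(115,000 − 65,000) = 40% for 2010–2013.

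**4. Spurious difference = gap × drift.** The protocol gives no yearly live birth trend; 0.5 to 1.0 point per year is an assumption.
- Denmark: 0.96 × 0.5 = 0.5 to 1.12 × 1.0 = 1.1 points.
- Sweden: 0.92 × 0.5 = 0.5 to 1.68 × 1.0 = 1.7 points.

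The gap is in cycle dates, while the yardstick is for MC-CLBR per woman, so the comparison is approximate. With year balanced by the weights, the gap and the spurious difference are zero in this set-up.

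**5. Effect on inference.** The standard errors at the step 1 sizes are 1.16 points (Denmark) and 0.80 points (Sweden). With no drug effect, a bias of 1 point raises the two-sided false-positive rate from 5% to about 14% and 24%.

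**6. HP-hMG.** The share of reference cycles before 2014 is (53,000 − 31,000)/53,000 = 41.5% in Denmark and (42,000 − 22,000)/42,000 = 47.6% in Sweden. For HP-hMG the figures give only bounds.
- Denmark: at most 58,000 − 31,000 − 5,000 = 22,000 cycles fall in 2014–2019, so at least 11,000/33,000 = 33% fall earlier. At most (42,000 − 22,000)/33,000 = 61% do.
- Sweden: by the same steps, 15,000/40,000 = 37.5% to 30,000/40,000 = 75%.

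The reference share lies inside both ranges, so even the sign of the time gap is undetermined.

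**The case against.** The plan is not blind to time. Study start dates differ by comparison. GnRH protocol, one of the four practice changes named in 9.1.1, is a PS variable and a stratifier. Cryopreservation method and days of embryo culture may be added to the outcome models. Sensitivity analysis 3 requires two years of follow-up for MC-CLBR and TTLB, and analysis 5b restricts Denmark to 2016–2020. All of this stands, but none of it balances calendar year: the added covariates are optional and measured after drug choice, analysis 3 only lengthens follow-up, and 5b concerns frozen-cycle linkage in one country. It is also fair that 9.1.1 does not date the practice changes within 2014–2019, and that the drift has no source in the protocol.

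Four stronger readings are tempting, and the document does not support them.
- A reader might infer that every comparison is shown to be confounded. For HP-hMG, 9.9.2 says only that prescribing probably varies, and step 6 fixes no direction.
- A reader might let reference use fall linearly to zero, giving a gap of L/3 = 1.92 years in Denmark. With an average share of about 54% (9.5) and even yearly cycle numbers, that fall would have to start at 2 × 54% = 108% of all cycles.
- A reader might see 9.9.5 as contradicting 9.1.1. Starting in 2010 to limit heterogeneity and then judging the remainder small is consistent; the fault is that the judgement is unsupported.
- A reader might cite the statement in 9.9.2 that "Prior to October 2016, induced abortions were not recorded in the SNPR". That bears on pregnancy loss and ongoing pregnancy, not on live birth, and Q-IVF still ascertains those events.

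**Conclusion.** The concern holds for the biosimilar comparison. The protocol documents that biosimilar use is concentrated late, expects success rates to change, already collects calendar year, and puts it in no model. The size rests on two assumptions, linear uptake from zero and a drift of 0.5 to 1.0 point per year. Under these the bias ranges from about a fifth (0.5/2.5) to under a half (1.1/2.5) of the stated detectable difference in Denmark, and from a quarter (0.5/2.0) to 85% (1.7/2.0) in Sweden, where the top of the range is a ceiling.

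The net direction is not known. Rising success rates would favour biosimilars; shorter follow-up of later cycles would favour the reference product on cumulative outcomes. For HP-hMG the plan leaves the comparison open to the same confounding, and nothing more can be said from the document.

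**What to change.** - In Table 1, mark calendar year of the stimulation cycle as a PS variable for both pairwise comparisons, entered as categories or a spline.
- Report its standardized difference after weighting, and check overlap in the first biosimilar years. Since potential follow-up is set by calendar date, balancing year would also largely balance follow-up time.
- In 9.9.5, replace the limited-impact statement with a reference to this adjustment.

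The cost is one table entry and a few sentences; no new data are needed. The downside is somewhat larger weights in 2014–2015, when biosimilar cycles are likely to be few. The weight checks, stabilization, trimming and truncation already foreseen in 9.7.3.1 can handle this.
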